5.4 Patient Participant Selection

5.4.1 Inclusion Criteria

1. Adult 18 years of age or older; and
2. Presenting with high-grade NMIBC established by anatomic pathology as tumor stage classification Tis, Ta, or T1, and with:
 - a. Pathology documentation from any hospital/clinic/medical center, and
 - b. More than 50% urothelial carcinoma component in the specimen
3. History of high-grade NMIBC established by anatomic pathology as tumor stage classification Tis, Ta, or T1; and
4. Attempted or received induction BCG (at least 3 out of 6 instillations) at any point in time; and
5. In the previous 12 months, received at least one instillation of any intravesical agent (induction or maintenance) or one administration of systemic therapy for NMIBC treatment.

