5.4.2 Exclusion Criteria

Participants must not have any of the following exclusion criteria:

1. Any plasmacytoid or small cell (neuroendocrine) component in the pathology (past or current presentation);
2. Previous history of cystectomy or radiation therapy for bladder cancer;
3. Previous history of muscle-invasive bladder cancer or metastatic bladder cancer;
4. Any history of upper tract urothelial carcinoma;
5. Incarcerated in a detention facility or in police custody (patients wearing a monitoring device can be enrolled) at baseline/screening;
6. Contraindication to radical cystectomy (e.g., ASA of 4, patient not considered a radical cystectomy candidate due to comorbidity);
7. Contraindication to medical management (i.e., intolerant of all medical therapies);
8. Unable to provide written informed consent in English;
9. Unable to be contacted for research surveys;
10. Planning to participate in a Phase I or Phase II interventional clinical trial for NMIBC (unless in the control/comparator arm of a Phase II trial) or any blinded interventional trial for NMIBC.

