## 1. General Design Considerations

### 1.1 Aims and Hypotheses

**Aim 1:** To compare patient-reported and patient-centered clinical outcomes between patients undergoing radical cystectomy and those receiving bladder-sparing therapies (BST) for NMIBC that have failed first-line BCG.

*Hypothesis 1.1: Patients undergoing radical cystectomy will have worse generic health-related QOL within 12 months of bladder removal surgery compared with BST patients.*

*Hypothesis 1.2: 12-month disease-free survival and metastasis-free survival will be better among radical cystectomy patients than among BST patients.*

*Hypothesis 1.3: Patient-reported and clinical outcome differences will vary within important subgroups including women, non-white patients, elderly patients, patients with multiple comorbid health conditions, patients with poor urinary function scores at the time of BCG failure, patients without caregivers, patients with atypical cancer histologies, and patients receiving investigational agents.*

**Aim 2:** To characterize the heterogeneity of treatments received and corresponding patient and caregiver preferences for NMIBC that have failed first-line BCG.

*Hypothesis 2.1: Patients who choose radical cystectomy for NMIBC with BCG failure will do so more often because they feel this offers their best chance for survival. Patients who choose BST will do so more often because they are concerned about the complications and QOL detriments associated with radical cystectomy.*

*Hypothesis 2.2: Patient and caregiver preferences will correlate strongly with observed treatments received and health-related QOL outcomes. We anticipate that QOL will vary by concordance of treatments received with treatment preferences and health state utilities.*

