### 4.1.1 Subgroups

Because each patient has a pair of potential outcomes under each treatment, we will include covariates in the TMLE and longitudinal data models to provide treatment effect estimates for important subgroups of interest stratified by age (75 or older vs. under 75), gender (males vs. females), patients who have a caregiver (yes vs. no), and cancer severity (carcinoma in situ vs not).

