## 6. Sample Size and Accrual

With recruitment of 572 participants, this study has  $>0.80$  statistical power to detect small differences in QOL between treatment approaches (Cohen's  $d = 0.24$ , or 5.5 points on the physical function scale of EORTC-QLQ-C30). Power analyses conservatively allowed for 10% missing data and assumed a correlation between repeated QOL measurements of 0.3. Assuming a similar balance of treatments within subgroups, this study also has  $>0.80$  power to detect moderate but clinically important treatment effects (Cohen's  $d = 0.43$ , or 9.9 points on the physical function scale of EORTC-QLQ-C30) within subgroups as small as 30% of the study cohort. Anticipated subgroups of this size include patients aged 75 years or older, women, and patients with multiple comorbid health conditions. For the secondary outcome of bladder cancer-specific mortality, data from a review combining multiple trials demonstrated an anticipated 1-year bladder cancer-specific mortality rate of 4.8% when treated with medical management. Assuming a 4.8% mortality rate in the medical management arm, this study has power to detect differences in 1-year bladder cancer-specific mortality rates of  $\leq 1\%$  in the radical cystectomy arm (power  $> 80\%$ ).

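### SAP 4.1.1 estimates effects in only three of the eight Hypothesis 1.3 subgroups; omitting comorbidity and investigational agents contradicts the protocol, and SAP 6 claims power for comorbidity

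*SAP*

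**What the plan says.** Hypothesis 1.3 appears in Protocol 3.0 and again in SAP 1.1. It names "women, non-white patients, elderly patients, patients with multiple comorbid health conditions, patients with poor urinary function scores at the time of BCG failure" and then "patients without caregivers, patients with atypical cancer histologies, and patients receiving investigational agents": eight groups in all.

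SAP 4.1.1 is the only place where the SAP specifies subgroup analyses. It lists estimates "stratified by age (75 or older vs. under 75), gender (males vs. females), patients who have a caregiver (yes vs. no" and by "cancer severity (carcinoma in situ vs not". Nothing in the sentence marks these four as examples.

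Other sections go further. SAP 6 claims more than 0.80 power at d = 0.43 in subgroups as small as 30% of the cohort and adds: "Anticipated subgroups of this size include patients aged 75 years or older, women, and patients with multiple comorbid health conditions". Protocol 9.2 plans treatment effects in the longitudinal model by age, comorbidity, caregiver status, tumor severity and investigational agents, given as examples. Protocol 9.4 adds an investigational-agent analysis if at least 10% of the medical management arm is in a phase III trial. It also gives SEER shares of 20% female, 52% over 75, 22% with a Charlson Index of 1 or more, and 25% with carcinoma in situ.

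**The concern.** The protocol's rationale (2.1) is to learn which patients are better served by cystectomy and which by medical management. Hypothesis 1.3 is the Aim 1 hypothesis that addresses this. Run as written, the SAP yields no effect estimate for most of the groups it names.

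Two of the gaps are also inconsistencies, because comorbidity and investigational agents are planned in the protocol but missing from the SAP's list. For urinary function, race and histology, neither document names a subgroup analysis or gives a definition, so any cut would be chosen at analysis. SAP 1.5 says the analysts are not blinded, and the SAP carries the same date as the first data freeze (March 14, 2024; SAP 1.6). A definition chosen later without a record would be hard to defend.

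**Working it through.** **Coverage.** Each Hypothesis 1.3 subgroup set against the places where an analysis, power statement or prevalence could appear:

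| Subgroup | SAP 4.1.1 | SAP 6 | Protocol 9.2 | Protocol 9.4 |
|---|---|---|---|---|
| Women | yes | named | no | 20% |
| Elderly | yes (75 or older) | named | age | 52% over 75 |
| No caregiver | yes | no | yes | no |
| Multiple comorbidity | **no** | named | yes | 22% (Charlson 1 or more) |
| Investigational agents | **no** | no | yes | if at least 10% of the arm |
| Poor urinary function | **no** | no | no | no |
| Non-white | **no** | no | no | no |
| Atypical histology | **no** | no | no | no |
| *Carcinoma in situ (not in Hypothesis 1.3)* | yes | no | tumor severity | 25% |

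Covered: 3 of 8. Not covered: 5 of 8 (62.5%). Of those five, two are planned elsewhere and three have no named analysis in either document.

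**Precision if comorbidity is added.** Inputs from Protocol 9.4: 235 cystectomy and 337 medical management patients, 10% missing, two-sided alpha 0.05, power 0.80, correlation 0.3. I assume a baseline-adjusted comparison, so the variance factor is 1 − 0.3² = 0.91.

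Detectable d = (1.960 + 0.842) × √[0.91 × (1/n₁ + 1/n₂)]

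1. Overall, to reproduce the plan's figure: n₁ = 0.9 × 235 = 211.5 and n₂ = 0.9 × 337 = 303.3, giving d = 0.2394. The plan states 0.24; power at 0.24 is 0.802.
2. With the same treatment balance in a subgroup of share p, divide by √p. At p = 0.30: 0.2394/0.5477 = 0.437 (stated 0.43; power at 0.43 is 0.787, slightly under 0.80).
3. At p = 0.22, the protocol's comorbidity share: 0.2394/0.4690 = **0.51**.
4. At p = 0.20, the share for women: 0.2394/0.4472 = 0.535.
5. If a urinary-function cut split the cohort in half (an assumption, since no cut is given): 0.2394/0.7071 = 0.339.

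The result at 22% is not sensitive to the variance assumption. An unadjusted calculation without missing data also reproduces the overall figure (0.238) and gives 0.508. Unadjusted with 10% missing gives 0.251 overall and 0.535 at 22%.

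SAP 6 equates d = 0.24 with 5.5 points, an SD of 5.5/0.24 = 22.9. So d = 0.51 is about 0.51 × 22.9 = 11.7 points, against the 9.9 points the SAP states for a 30% subgroup.

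**Difference between subgroup and complement.** This is what a hypothesis of varying effects concerns. Its detectable size is 0.2394/√[p(1 − p)], which at p = 0.22 is 0.2394/0.4142 = 0.58.

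**The case against.** A short subgroup list can be good practice. At 22% prevalence the detectable effect of 0.51 is slightly above the 0.5 that Protocol 9.4 calls the minimally important difference, and every added subgroup is another chance for a spurious finding. This stands as a reason to report estimates with intervals rather than tests. It does not explain why SAP 6 claims power for a subgroup that SAP 4.1.1 leaves out, or why the hypothesis still names eight.

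A reader might infer several stronger points that the documents do not support:

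- *That every later estimate would be post hoc.* Not for comorbidity or investigational agents: Protocol 9.2 already commits to both. There the defect is a mismatch between protocol and SAP.
- *That urinary function is never measured at the relevant time.* Protocol 5.2 enrolls patients whose BCG has failed and who are weighing second-line treatment, and Table 1 collects the Bladder Cancer Index at baseline. The unrestricted timing in Protocol 5.4.1 applies to induction BCG, not to the failure. Later non-BCG therapy can separate the two dates, but baseline is a reasonable proxy. What is missing is a statement to that effect and a cut.
- *That eligibility removes most of the atypical-histology group.* Protocol 5.4.1 requires "More than 50% urothelial carcinoma component in the specimen" and Protocol 5.4.2 excludes "Any plasmacytoid or small cell (neuroendocrine) component in the pathology (past or current presentation". These narrow the group, but neither document says by how much, and specimens with another minority component remain eligible.
- *That carcinoma in situ is an unplanned addition.* It is absent from Hypothesis 1.3, but Protocol 9.2 names tumor severity and Protocol 9.4 lists carcinoma in situ.
- *That a Charlson Index of 1 or more is the plan's comorbidity definition.* It is given only as a SEER prevalence, and a single condition may meet it.

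**Conclusion.** The point holds as a gap and an inconsistency in the SAP. SAP 4.1.1 covers three of the eight Hypothesis 1.3 subgroups and omits five. The comorbidity omission conflicts with Protocol 9.2 and SAP 6. The investigational-agent omission conflicts with Protocol 9.2 and the 10% condition in Protocol 9.4. The primary comparison is untouched, so this should be corrected but does not threaten the main result.

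The count needs no assumption beyond reading SAP 4.1.1 as the complete list, which its wording supports. The d = 0.51 rests on three assumptions: the 22% SEER share applies to this cohort, treatment balance is similar within the subgroup, and the outcome analysis is baseline-adjusted. A definition requiring several conditions could give a different share. SAP 6 treats women and multimorbid patients as subgroups of about 30%, while the protocol's figures are 20% and 22%. At those shares the stated 0.43 is below what the study can detect with 0.80 power.

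**What to change.** Issue a dated, labelled SAP addendum that states its timing relative to the March 14, 2024 freeze and adds to SAP 4.1.1:

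- **Comorbidity**, with one stated definition built from the baseline comorbidity data.
- **Urinary function**, using the baseline Bladder Cancer Index score, with a sentence saying that baseline stands for status at BCG failure and with the cut or continuous form fixed in advance.
- **Non-white versus white**, assuming race is collected under Demographics in Table 1.
- **Investigational agents**, under the protocol's condition (10% of 337 is about 34 patients). Because Protocol 5.1 places these agents in the medical management arm, state which cystectomy patients form the comparison.

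Report each as an estimate with its interval. For atypical histology, define the group or state that it is descriptive only. Note that carcinoma in situ comes from the protocol's tumor-severity subgroup and not from Hypothesis 1.3. Align the prevalences in SAP 6 with Protocol 9.4.

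The cost is SAP wording and a few more runs of the same models, mostly on baseline data already scheduled. The downside is more subgroup estimates to interpret, some of them imprecise.

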## 4.2 Secondary Outcomes

Other patient reported outcomes will be evaluated using a similar analytic framework to the primary outcome. To test the hypothesis that cancer-specific survival will be better in patients undergoing radical cystectomy, we will use a superiority testing framework. For assessment of time-to-event outcomes we will use inverse probability weighted Cox proportional hazards models to estimate relative risks. Survival outcomes will be censored at the time of the last study contact or clinic visit for patients who are lost to follow-up and have no recent EHR-verified clinic visits. Since time-to-event outcomes (cancer-specific survival and metastasis-free survival) will be highly correlated with one another, two-sided 95% confidence intervals will be used for inference without adjustment for multiple survival endpoints.

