6.3 Patient Follow-up Assessments

The patient follow-up assessments should be completed in-person, online, by phone, or by mail. The measures included at each time point are listed in Tables 1 and 2, if participating in the extended/long-term follow-up. UW study staff will contact the participant to complete the follow-up assessments. Outreach will include a combination of phone, mail, and email as determined by the contact information provided by the participant. If the contact protocol is exhausted and the assessment has not been completed, a research coordinator at the participant's enrollment site will be notified. They will review the EMR and provide any site-specific or EMR-specific updates that may be helpful; for example, an updated telephone number. Additional contact attempts (calls, emails, texts, etc.) may be attempted from the local site coordinators. If the assessment is still not completed, it will be considered missed and attempts to contact the participant will resume at the next assessment time point.

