6.6 Electronic Medical Record Abstraction

Patients consenting to the study will have their EMR reviewed at pre-determined time points. Research coordinators will conduct an EMR review at baseline and for subsequent healthcare utilization events and clinical outcomes. Data collected will include variables relating to health history, transurethral resection of a bladder tumor (TURBT), medical management, laboratory values, imaging results, pathology findings, cystectomy, and adverse events.

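### SAP 4.2 uses one censoring rule for all survival outcomes, so for patients lost to follow-up a survey date can extend metastasis-free time beyond the last disease assessment

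*SAP*

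**What the plan says.** SAP 4.2 gives this rule for time-to-event outcomes: "Survival outcomes will be censored at the time of the last study contact or clinic visit for patients who are lost to follow-up". The sentence continues "and have no recent EHR-verified clinic visits", so both conditions must hold. It is the only censoring rule in that section. The same paragraph names the outcomes in view: "time-to-event outcomes (cancer-specific survival and metastasis-free survival) will be highly correlated with one another". They are analysed with "inverse probability weighted Cox proportional hazards models to estimate relative risks".

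Protocol 6.3 describes the study contacts: "UW study staff will contact the participant to complete the follow-up assessments", and "The patient follow-up assessments should be completed in-person, online, by phone, or by mail". Protocol Tables 1 and 2 list what these contacts collect. All the items are questionnaires or self-reported history, with no imaging or clinical examination. Disease status comes by another route. Protocol 6.6 has site coordinators abstract data from the medical record, including "laboratory values, imaging results, pathology findings, cystectomy, and adverse events".

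Metastasis-free survival is named in Hypothesis 1.2 (Protocol 3.0, SAP 1.1). SAP 3 lists it as a secondary outcome and plans to follow it to 48 months and for up to six further years.

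**The concern.** A contact date is a sound censoring date for death, because a patient who answers a survey is known to be alive. It is not in itself a sound date for metastasis-free survival. A patient who has stopped attending the clinic but returns a questionnaire has been observed for survival and not examined for metastasis. If that date is used, the interval since the last disease assessment enters the denominator although a metastasis in it could easily go unrecorded. The event rate is then too low and metastasis-free survival too high.

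The second condition in the rule does not remove the problem. It selects patients without a recent verified visit, for whom a survey is most likely to be the later date.

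At stake is the metastasis-free half of Hypothesis 1.2. If the arms differ in how long patients answer surveys after leaving clinic follow-up, the comparison is affected too. The room for such gaps grows after month 12. Surveys become six-monthly and then annual, and the documents do not specify when medical record reviews take place.

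**Working it through.** The documents give no event rate, effect size or power for metastasis-free survival, so there is no stated figure to reproduce. The check has two parts.

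**Reading the rule**

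1. Metastasis-free survival falls under the SAP 4.2 rule, because it is named there and no other rule is given.
2. The rule allows a study contact as the censoring date, and under Protocol 6.3 a contact may be by phone, mail or online.
3. No scheduled contact includes a disease assessment (Protocol Tables 1 and 2). Imaging and pathology come from Protocol 6.6.
4. A survey date later than the last disease assessment can therefore become the censoring date. The rule joins contact and clinic visit with the word or, and does not say which governs when both exist. Two analysts could censor the same patient on different dates.

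**Size, on assumed inputs**

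Taken from the documents: allocation 337 medical management (bladder-sparing therapy, BST) to 235 cystectomy (Protocol 9.4), and the 12-month horizon. Everything else is assumed:

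- a true 12-month metastasis risk *p* in the BST arm of 5% or 10%;
- a true hazard ratio (cystectomy to BST) of 0.50, with exponential event times;
- a share *L* of patients who stop clinic visits at a time uniform over 0-12 months, yet answer surveys to month 12. This is the longest possible gap.

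Affected patients are observed for disease for half of the 12 months on average, so the event rate is multiplied by about 1 − *L*/2. Then:

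- estimated risk ≈ 1 − (1 − *p*)^(1 − *L*/2)
- estimated hazard ratio ≈ 0.50 × (1 − *L*(cystectomy)/2) / (1 − *L*(BST)/2)

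With *p* = 10%:

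- *L* = 5%: 1 − 0.90^0.975 = 9.8%
- *L* = 20%: 1 − 0.90^0.90 = 9.0%

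For the hazard ratio with unequal shares:

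- 5% BST, 20% cystectomy: 0.50 × 0.900/0.975 = 0.46
- 15% BST, 5% cystectomy: 0.50 × 0.975/0.925 = 0.53

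A large simulation of the same set-up agrees to within about 0.1 percentage point for risk and 0.005 for the hazard ratio:

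| Affected, BST / cystectomy | BST risk if true 5% | BST risk if true 10% | Hazard ratio (true 0.50) |
|---|---|---|---|
| 5% / 5% | 4.9% | 9.8% | 0.50 |
| 20% / 20% | 4.5% | 9.1% | 0.50 |
| 5% / 15% | 4.9% | 9.8% | 0.48 |
| 5% / 20% | 4.9% | 9.8% | 0.46-0.47 |
| 15% / 5% | 4.7% | 9.3% | 0.53 |

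Censoring the same simulated patients at their last clinic visit returned risks of 5.0% and 10.0% and a hazard ratio of 0.50.

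A cruder measure is the share of the 12 months' person-time that is unobserved, which equals share affected × gap in years. It runs from 0.05 × 0.25 = 1.25% to 0.20 × 0.75 = 15%. The top is a corner case. The last survey before month 12 is at month 9, so a nine-month gap means either no disease assessment after baseline, or a month-12 survey with the last assessment by month 3.

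**The case against.** The strongest reply is that the rule is narrow. It applies only to patients who are lost to follow-up and also have no recent verified visit. Someone who keeps answering surveys is not obviously lost, so the scenario above may describe more patients than the rule governs. This stands as a limit on the size. It does not remove the problem, because a patient may answer for some months after the last clinic visit and then be lost.

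Contacts are also not blind to disease. Surveys from month 3 ask about healthcare use, and under Protocol 10.1 a reported hospitalization or death leads to an adverse event form completed from the medical record. A reader might infer that no event can be recorded after the last clinic visit. The documents do not support that. A metastasis that produces no such event could still be missed. Metastasis-free survival is not defined either, and if it includes death, contacts capture part of it.

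Two other strong readings should be set aside. One is that the last contact is often only a survey. No passage gives a frequency, and assessments may be done in person. The other is that unassessed patients are counted as metastasis-free. They are censored, and count as event-free only up to the contact date.

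Finally, censoring at assessments has its own weakness. No imaging schedule is given, so assessment timing may differ by arm and could be informative. That is a reason to restrict the change to lost patients and to keep the present rule as a sensitivity analysis.

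**Conclusion.** The point holds in a limited form. SAP 4.2 applies to metastasis-free survival a censoring date that establishes vital status but not disease status, and leaves open which of two dates governs. Where a later survey date is used, the direction is predictable: metastasis-free survival is overstated. The likely size is small. With 5-20% of patients affected and the longest possible gap, a 10% risk is read as about 9.8-9.1%, and a 5% risk as about 4.9-4.5%. These shares and risks are assumptions, since the documents give no rate of loss from clinic follow-up.

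A reader might infer that the treatment comparison is biased. That follows only if the gap differs by arm, and the documents give no evidence that it does. With equal gaps the hazard ratio stays at 0.50. With the unequal gaps tried it moves to between about 0.46 and 0.53. The primary endpoint, physical functioning at 12 months, is untouched, and the rule is sound for death outcomes. The change is still worth making, because the outcome belongs to a named hypothesis and the correction is cheap.

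**What to change.** Split the rule in SAP 4.2:

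- For death outcomes, keep censoring at the last study contact or clinic visit.
- For metastasis-free survival, and for any disease-free or progression outcome, censor event-free patients who are lost to follow-up at the last disease assessment documented in the medical record: imaging, pathology, or a clinic visit with disease evaluation.
- State that this date governs when a later survey exists.
- Report the gap between last assessment and last contact by arm, and repeat the analysis with last-contact censoring as a sensitivity analysis.

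The cost is a few sentences in the SAP and slightly less follow-up time for these outcomes. No new patient procedures are needed, and the change can be applied when the final data set is generated (SAP 1.6). One thing must be checked first. Protocol 6.6 lists results and findings but does not mention their dates, so the availability of assessment dates in the abstraction has to be confirmed.
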